6.2 Dose, Packaging and Labelling

The interventions will be supplied to sites in HDPE DUMA bottles with child-resistant, tamper evident caps. Each bottle will contain 5 capsules. The information presented on the IMP labels will be annex 13 compliant.

Trial participants will receive five capsules of the Investigational Medicinal Product (IMP) to be taken orally at a hospital clinic every 91 days +/- 14 days for a total of 21 months.

Trial participants are recommended to fast for 4-hours prior to treatment. Light snack is allowed if medically advised and fasting requirements will be under the PI's discretion. At each treatment dose, the participant will be able to fast prior to their hospital visit and the fasting duration will be captured on the database. The fast is to facilitate absorption of the IMP and reduces the likelihood of participant vomiting after IMP administration. They will be requested to ingest all capsules within 30 minutes and are permitted unlimited water or squash.

Trial participants who are unable or are unwilling to ingest the IMP will be withdrawn from the study and the reasons will be recorded.

Trial participants who are unable to swallow all 5 capsules or are only able to swallow 1 or more of the capsules but not all 5 will continue to be followed-up as per the study schedule but this will be recorded in the eCRF.

Trial participants with alcohol-related or MASLD-ALD Overlap cirrhosis must be abstinent for a minimum of 4 weeks prior to randomisation and are encouraged to remain abstinent from alcohol for the duration of the trial (abstinence from alcohol in this group of patients is considered standard of care regardless of enrolment into a clinical trial). If the participant relapse back to drinking alcohol, they will still be included in the trial and continue to receive IMP as per schedule. Relapse to drinking alcohol will be assessed as a secondary endpoint with the AUDIT questionnaire.³³

Trial participants must not have received antibiotics within 7-days prior to randomisation and at each dosing visit. The routine prescription of prophylactic antibiotics including ciprofloxacin and co-trimoxazole (prophylaxis of spontaneous bacterial peritonitis) and rifaximin (hepatic encephalopathy) will not be permitted at randomisation as they will reduce the efficacy of the FMT and will exclude a patient from the trial if the treating physician deems ongoing treatment is necessary. If at randomisation a participant is deemed likely to need to remain on the long-term antibiotics, then they should be excluded as this will impede the efficacy of the IMP. If any antibiotic is later clinically indicated during the course of the study for the treatment of suspected or confirmed infection, or rifaximin for the treatment of recurrent overt hepatic encephalopathy, then these will be permitted to be

given as standard of care. If the participant is receiving short term antibiotic treatment, there will be a 7-day washout period before continuing IMP per dosing schedule. If the participant is receiving long-term antibiotic treatment, the participant will continue to receive IMP as per the dosing schedule. The participant will no longer receive further IMP doses if they have been hospitalised for an infection and have met the primary endpoint.

The development of infection resulting in hospitalisation will meet the primary endpoint and the participant will no longer receive further IMP doses, although they will continue to be followed up for the duration of the trial.

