7.7 Withdrawal of Participants

A trial participant has the liberty to withdraw their consent at any time and for any reason, without penalty or loss of benefits to which the individual would otherwise be entitled. Participants who withdraw consent will discontinue their future participation in the trial, but we will request to collect future routine outcome data from the patient notes (*e.g.*, hospitalisation due to infection). Prior to giving consent, recipients will be informed that they are able to request the destruction of stored biological samples (*e.g.*, blood/stool) upon withdrawal, and that this will only be possible for samples that have not been tested at the time of withdrawal. Participants will not be able to request the deletion of data generated from tested samples.

Participants have the right to withdraw from the study at any time for any reason. The investigator also has the right to withdraw participants from the study drug in the event of intercurrent illness, AEs, SAEs, SUSARs, protocol violations, cure, administrative reasons or other reasons. It is understood by all concerned that an excessive rate of withdrawals can render the study un-interpretable; therefore, unnecessary withdrawal of participants should be avoided. Should a participant decide to withdraw from the study, all efforts will be made by the investigator to report the reason for withdrawal as thoroughly as possible.

The investigator will maintain a record of all participants who discontinue from the trial prior to completion: the reason(s) for trial discontinuation will be documented. In the event, a participant wishes to discontinue the treatment (i.e., withdraw from the study drug only), efforts will be made to continue to obtain follow-up data by encouraging participants to attend the follow-up visits.

Participants who wish to withdraw from trial medication (IMP) only will be asked to confirm whether they are still willing to provide the following:

- trial-specific data at follow-up visits including safety and adverse event monitoring.
- data collected as per routine clinical practice at visits.
- Withdrawn participants will not be replaced.

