11.3 Analysis

Primary Outcome: The number of days from randomisation to first infection ³² leading to hospital admission.

Assessment of efficacy:

The main analysis will include all randomized participants (eligibility as defined in section 7) in the arms to which they were randomized, regardless of what treatment they received postrandomisation, with the intent to estimate an intention-to-treat (ITT) type estimand. For the primary analysis, a treatment policy strategy will be used for any intercurrent events (such as discontinuation of treatment or death), that is the occurrence of the intercurrent event will be considered irrelevant in defining the treatment effect of interest. Sensitivity analyses will examine this assumption using different strategies for the intercurrent events. Population definitions, target estimands and handling of intercurrent events will be further described in the Statistical Analysis Plan.

Primary analysis: A Cox baseline proportional hazards model of the time to infection will be fitted with frailty effect to account for site heterogeneity, adjusted for baseline disease severity, participant age, sex and baseline cirrhosis severity. The adjusted hazard ratio will be presented with associated 95% confidence interval. Proportionality will be assessed using a Kaplan Meier survival and log-log plots.

Secondary analysis:

Time to event outcomes including mortality (all-cause; liver-related), hospitalisation, progression to ACLF ³³ and hepatic decompensation will be analysed in a manner consistent with the primary analysis.

Binary outcomes (infection rates, AMR incidence and antibiotic usage) will be analysed with a mixed-effects multivariable logistic regression, fitting a random effect for site, and fixed effects for: participant age, sex, baseline disease severity.

Continuous outcomes (liver disease severity scores; AUDIT score; HADS score; EQ-5D-5L score) will be analysed using a mixed effects multivariable regression, adjusted in a consistent manner with the primary outcome analysis including baseline version of the outcome if applicable.

Missing data and population under investigation:

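### Section 6.2 ends follow-up for randomised participants who do not take the capsules, contradicting Section 7.7 and the treatment-policy analysis in Section 11.3

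*Protocol*

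**What the plan says.** Section 6.2 (Dose, Packaging and Labelling) has one rule for complete non-ingestion: "Trial participants who are unable or are unwilling to ingest the IMP will be withdrawn from the study and the reasons will be recorded". The paragraph after it deals with participants who manage only some of the five capsules, and says that they "will continue to be followed-up as per the study schedule but this will be recorded in the eCRF". The same section stops the capsules once the primary endpoint is met, "although they will continue to be followed up for the duration of the trial".

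Section 6.6 (Participant Compliance) treats an incomplete dose or a missed visit as a protocol deviation to be recorded, not as a withdrawal.

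Section 7.7 (Withdrawal of Participants) separates leaving the trial from stopping the study drug. For those who stop the drug only, "efforts will be made to continue to obtain follow-up data by encouraging participants to attend the follow-up visits". For those who withdraw consent, "we will request to collect future routine outcome data from the patient notes". It adds: "Withdrawn participants will not be replaced".

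Section 11.3 (Analysis) sets the primary analysis: "The main analysis will include all randomized participants (eligibility as defined in section 7) in the arms to which they were randomized". Whether a participant took the capsules makes no difference to inclusion, which holds "regardless of what treatment they received postrandomisation". The section applies a treatment policy strategy to intercurrent events and names discontinuation of treatment as one of them.

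**The concern.** A treatment policy estimand needs the outcome after the intercurrent event. Section 6.2 tells sites to withdraw a participant from the study at exactly such an event. A site that follows it will stop collecting data that Section 11.3 needs, and the statistical analysis plan cannot recover data that were never collected.

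The loss may also be informative. Someone who cannot or will not swallow the capsules may be sicker, or may have tolerated an earlier dose badly, and either could be related to the risk of infection. If refusal differs by arm, censoring at refusal can move the hazard ratio. Mortality and 24-month safety, both listed in Section 5.3, would be lost for the same people.

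**Working it through.** **1. Does the rule reach randomised participants?** Section 8.1.3 randomises when the participant arrives for dosing; dispensing and ingestion follow. Exclusion 14 screens for likely inability or unwillingness, but only before randomisation. So the Section 6.2 rule acts on people already in the primary population.

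**2. The rules side by side.**

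| Situation | Section | Follow-up |
|---|---|---|
| Takes no capsules | 6.2 | Withdrawn from study |
| Takes some capsules | 6.2 | Continues |
| Capsules stopped after primary endpoint | 6.2 | Continues |
| Incomplete dose or missed visit | 6.6 (Participant Compliance) | Recorded as deviation |
| Stops study drug only | 7.7 | Sought |
| Withdraws consent | 7.7 | Notes data requested |
| Primary analysis | 11.3 | All randomised, whatever treatment was taken |

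The first row stands alone. A participant who attends and declines is handled more strictly than one who does not attend.

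**3. The plan's own sample size (Section 11.1).** Inputs: hazard ratio 0.625, alpha 0.047 (taken as two-sided), 80% power, two-year event proportions 65% and 48.9%, 10% loss.
- Freedman events: ((1 + 0.625)/(1 − 0.625))² × (1.986 + 0.842)² = 150.2, so 151, against 155 stated.
- Mean event proportion: (0.65 + 0.489)/2 = 0.5695. Events from 270 patients: 270 × 0.5695 = 153.8.
- Inflation: 270/0.90 = 300, as stated.

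The figures reproduce to within 3%, and this point does not dispute them.

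**4. Events lost.** The protocol gives no rate of non-ingestion, so 5% is an assumption: 300 × 0.05 = 15 participants.
- Upper bound, all refuse at day 0 and nothing is recovered from notes: 15 × 0.5695 = 8.5 events.
- Refusals spread evenly over the eight dosing visits (months 0, 3, …, 21), each participant event-free at refusal, exponential hazards. Monthly hazards are −ln(0.35)/24 = 0.0437 (placebo) and −ln(0.511)/24 = 0.0280 (FMT). The chance of an event between month t and month 24 is 1 − exp(−h(24 − t)). Averaged over the arms, this falls from 0.5695 at month 0 to 0.102 at month 21; the mean over the eight visits is 0.361. Then 15 × 0.361 = 5.4 events.

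**5. Power.** Schoenfeld: Φ(½√events × |ln 0.625| − 1.986), taking the lost participants to contribute no events.

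| Extra loss on top of 10% | Participants | Events | Power |
|---|---|---|---|
| 0% | 270 | 153.8 | 82.3% |
| 5% | 255 | 145.2 | 80.1% |
| 10% | 240 | 136.7 | 77.7% |
| 15% | 225 | 128.1 | 75.0% |

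If these withdrawals already sit within the 10%, planned power does not change.

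**6. Bias, illustration only.** Assume no true effect, a 65% two-year risk in both arms, withdrawal at day 0 of 5% to 15% of the FMT arm only, and an infection hazard in those withdrawn of 1 to 2 times that of the rest. The apparent hazard ratio is taken as the cumulative hazard of those remaining divided by −ln(0.35) = 1.050.

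| Withdrawn, FMT arm only | Hazard × 1 | × 1.5 | × 2 |
|---|---|---|---|
| 5% | 1.00 | 0.98 | 0.97 |
| 10% | 1.00 | 0.96 | 0.94 |
| 15% | 1.00 | 0.94 | 0.91 |

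The shift here favours FMT. Withdrawal confined to the placebo arm would push the other way.

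**The case against.** The strongest reply is that this is loose wording and not a rule that costs data. The paragraph on partial dosing opens with people unable to swallow all five capsules, which could be read to include those who swallow none. Section 6.2 names no visit. Exclusion 14, and randomising only when the participant arrives for dosing, should keep first-dose refusals rare. The endpoint is a hospital admission, and Section 7.7 seeks routine outcome data from notes even after consent is withdrawn.

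Part of this stands. Refusals may be few, and notes review could recover some admissions. But the notes request is written for participants who withdraw consent, not for those whom the protocol itself withdraws. Exclusion 14 acts only before randomisation. If the partial-dosing paragraph does cover those who take nothing, Section 6.2 contradicts itself within two paragraphs, and the text still has to be reconciled.

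A reader might infer more than the document supports:
- **That these participants leave the analysis set.** Section 11.3 keeps all randomised participants. They would be censored at withdrawal, events before that still count, and only later ones can be lost.
- **That the primary analysis becomes close to an on-treatment one.** Partial dosers, participants whose capsules stop after the endpoint, and those who relapse to drinking or start long-term antibiotics all stay in follow-up.
- **That the complier analysis loses its non-compliers.** Adherence is set at more than 70% of the allocated intervention, so many partial takers also count as non-adherent and are still followed.
- **That loss will differ by arm.** Section 6.3 says most reported FMT side effects are gastrointestinal, but Section 4 reports no excess of these over placebo in the endoscopic feasibility trial (15 treated) and describes capsules as well tolerated in a 10-patient study. Differential loss is possible, not shown.

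**Conclusion.** The contradiction is real, and the text is wrong as written: Section 6.2 cannot be followed together with Section 7.7 and the treatment policy strategy of Section 11.3. The effect on power is small. At an assumed 5% non-ingestion, between about 5.4 events (refusals spread over the dosing visits) and 8.5 events (all at day 0, an upper bound) are lost, out of roughly 154 expected. Power is 80.1% if this comes on top of the planned loss, and unchanged if within it.

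The case for change rests on avoidable and possibly informative missing outcomes. The bias figures depend wholly on assumed rates, arm imbalance and hazard, so they show what could happen and do not predict it. The sponsor should correct this, because the correction is simple and the data cannot be recovered afterwards.

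**What to change.** Reconcile Sections 6.2, 6.6 (Participant Compliance) and 7.7, and replace the withdrawal wording in Section 6.2 with a statement about follow-up only. For example: *non-ingestion and its reasons will be recorded, and the participant will remain in follow-up for all outcomes to month 24 as in Section 7.7, unless consent for follow-up is withdrawn.* Whether such a participant is offered further doses is a separate matter for the sponsor, and this wording should not settle it.

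The cost is a protocol amendment, which Section 16 requires to go to the ethics committee and regulators, plus follow-up of these participants at visits already in the schedule. No change to the sample size or the analysis is needed.

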6.3 IMP Risks

In 2015, the UK Human Tissue Authority (HTA) published an opinion that FMT does not fall within the scope of the UK Human Tissue (Quality and Safety for Human Application) Regulations 2007, but also recommended that establishments conducting FMT should act in accordance with the HTA "Guide to Quality and Safety Assurance for Tissues and Cells" for patient treatment. The Medicine and Healthcare Products Regulatory Agency (MHRA) classifies FMT as a medicinal product. All medicinal products should be produced according to the principles of GMP under MHRA licence.

FMT is a heterogenous product, whose mechanism of action remains to be ascertained. As such it is difficult to assess the risks associated with FMT administration. The main concern relating to FMT is the potential for transmissible infection.

The majority of reported side effects from FMT are gastro-intestinal and short-lived/selflimiting. ²⁰ The side effects also relate to route of administration *e.g.* endoscopy. As a result of the encapsulated formulation, there is no need for endoscopic administration of FMT. Two cases of extended spectrum beta-lactamase (ESBL) producing *E. coli* bacteremia have been reported in immunocompromised patients (one with hepatitis C cirrhosis and one with myelodysplastic syndrome, post stem cell transplant) in the USA, linked to a single donor FMT. The patient with myelodysplastic syndrome sadly died as a result of his infection. ⁴⁰ Prior to this, FMT was not screened for ESBL-producing organisms in the USA. The Food and Drug Administration (FDA) halted FMT trials temporarily as a result and ESBL screening in the USA is now mandatory. Our FMT is routinely screened for ESBL and carbapenemase producing organisms and aliquots of donor stool are stored for 30-years for full traceability.

To minimise risk, the FMT laboratory at GSTT will be used to manufacture FMT, which holds a MHRA Manufacturer's Authorisation for Investigational Medicinal Products (MIA(IMP)) and complies with MHRA rules and guidance for Pharmaceutical Manufacturers and Distributors (Orange Guide, 2017), in accordance with GMP.

FMT is endorsed by NICE ²³ for the treatment of recurrent *C. difficile* infection and has been successfully used to treat over 250 patients at GSTT. **15 participants with cirrhosis** received FMT as part of the PROFIT trial (NCT02862249). ²⁷ There were no IMP-related serious adverse events.

Please refer to the Investigators Brochure, which contains the reference safety information for the FMT product.

6.4 Drug Accountability

The pharmacy clinical trials team must maintain accurate accountability records of the IMP, which will be reviewed by the trial CRA for monitoring purposes.

Following participant administration with the IMP, the IMP bottle and any unused capsules must be disposed of in the clinic room in clinical waste bins/bags. The packaging and unused capsules do not need to be returned to pharmacy for reconciliation and disposal. The number of capsules administered, and number of capsules discarded will be recorded and verified for monitoring purposes.

The disposal of unused IMP stored in pharmacy (*i.e.*, damaged/ expired stock, or stock remaining at the end of the trial) is only permitted with written Sponsor approval and CI authorisation. Do not destroy unused study drug without prior authorisation from the Sponsor. Once authorised, destruction can be conducted at site in accordance with the site IMP destruction SOP and disposed of in accordance with the hospitals clinical waste procedures.

6.5 Storage and Supplies

6.5.1 FMT:

Store the FMT product in a locked freezer at:

• -20°C (range -25°C to -15°C),

An automated electronic temperature monitoring system/device must be used at sites for temperature monitoring and reporting.

In the event of a temperature excursion, quarantine the supplies and notify the Sponsor immediately following the instructions in the Pharmacy Manual.

Supplies that are in quarantine, must be clearly segregated from stock that is available for allocation.

FMT capsules thaw quickly once they are removed from the freezer and come to room temperature within 5-minutes. Once the product is removed from frozen storage at the point of dispensing, it must be either administered within 6 hours or quarantined (in pharmacy) or disposed of (in clinic); it cannot be refrozen.

6.5.2 Placebo:

Store the placebo product in a secure location at room temperature maintaining the temperature at less than 30°C.

Temperature monitoring and reporting is required. In the event of a temperature excursion, quarantine the supplies and notify the Sponsor immediately following the instructions in the Pharmacy Manual.

6.5.3 Supplies:

The site pharmacy teams will be unblind to a participant's treatment allocation. The trial centre pharmacy will dispense the correct treatment arm in accordance with the unblinded

randomisation notification on receipt of a trial-specific prescription which has been signed by a prescriber on the site delegation log.

The Kings Clinical Trials Unit (KCTU) Intervention Management System will be used to manage supplies centrally and at study sites. The KCTU Trials Pharmacist will place the initial order and subsequent orders to restock sites with the interventions.

6.6 Participant Compliance

Participants will take their IMP at their hospital outpatient visits so adherence will be directly observed. The number of capsules taken by the participant will be recorded in the CRF. If the participant is unable to take the full dose or capsules are damaged/dropped the reason for the deviation from the protocol will be recorded in the CRF and on a deviation log which is filed in the ISF. If a participant misses their visit or is outside the window for the visit, we will still give them the dose and record it as a protocol deviation.

6.6 Concomitant Medication

Specific concomitant medications including antibiotics (as part of standard of care), beta blockers (Carvedilol and Propranolol), Lactulose (prebiotic), probiotics, anti-depressants/anti-anxiety/psychiatric medication and proton pump inhibitors (PPI) received during the treatment phase will be recorded in the relevant CRF for this trial.

Trial participant must not have received antibiotics within 7 days prior to randomisation and at each dosing visit.

The routine prescription of prophylactic antibiotics including ciprofloxacin and co-trimoxazole (prophylaxis of spontaneous bacterial peritonitis), rifaximin (hepatic encephalopathy) and probiotics (other than foods)* will not be permitted at randomisation as they may reduce the efficacy of FMT and will exclude a participant from the trial if the treating physician deems ongoing treatment is necessary. If any antibiotics is later indicated during the course of the study for the treatment of suspected or confirmed infection, or rifaximin for the treatment of recurrent overt hepatic encephalopathy, then these will be permitted to be given as standard of care.

If a participant has been treated with antibiotics for an acute infection following commencement of IMP which did not necessitate hospital admission *i.e.*, did not meet primary endpoint, then repeat dosing will be delayed until 7 days following finishing the antibiotic course. If, however the participant has been commenced on long-term prophylactic antibiotics as part of their standard clinical care that will continue for the remaining duration of the trial including ciprofloxacin and co-trimoxazole (prophylaxis of spontaneous bacterial peritonitis) and rifaximin (hepatic encephalopathy), then participants will be permitted to receive their IMP as per dosing schedule. If antibiotics are given during hospital admission due to infection then the participant has met the primary endpoint. This would result in discontinuation of IMP but the participant would remain in the study for follow-up.

Specifically, participants will not be required to follow a specific diet, nor will they be required to use contraception (FMT is not known to be teratogenic). Please refer to the Investigators Brochure for further safety data.

King's College Hospital

*There are no universally accepted definitions of probiotics, and there is a plethora of products available. These substances are often contained in several commonly consumed foodstuffs *e.g.*, yoghurt, cheese, beer etc. For the purposes of this study participants who consume foodstuffs containing probiotics will not be excluded from the trial, other products will be reviewed on a case-by-case basis. A rule of thumb to aid decision making is to allow products that can be found in the food aisles of supermarkets and exclude products that can found in the pharmacy/health products or vitamins aisle.

7 Selection and Withdrawal of Participants

Eligibility screening of the patients will be carried out by a research nurse at each clinical site who will evaluate the following inclusion and exclusion criteria. This will then be reviewed and approved by the Site Principal Investigator (PI).

